9.3 Sample size calculation

The sample size for the Part 1 dose-escalation portion and Part 2 schedule-escalation portion of the study will be determined by the number of escalation steps and the required sample within cohort (3 or 6 patients). The sample size for the expansion phase will be chosen to assist in determining whether sufficient preliminary evidence of efficacy is seen to justify further study. If at least 4 of the total of 18 patients enrolled at the RP2D achieve a response or have stable disease for at least 3 months, the statistical basis of evidence will be satisfied. This schema will use a promising ORR/SD of 30% and an uninteresting ORR/SD of 10%, with a one-sided α -level of 0.10 and power of 80%. Note that durable stable disease of 30% is also a promising outcome.

The following table gives the probability of dose escalation as a function of the true DLT probability:

True Probability of DLT	0.05	0.1	0.2	0.3	0.4	0.5	0.6	0.7
Probability of Escalation	0.97	0.91	0.71	0.49	0.31	0.17	0.08	0.03

For Part 4 (Cohort 11), the sample size was chosen to support the primary objective of assessing clinical response in patients with relapsed or refractory ES (including patients with ESFT) to assist in determining whether sufficient preliminary evidence of efficacy is seen to justify further study.

With a hypothesized ORR of 25% and an unacceptable (null) ORR of 5%, a sample size of 21 patients achieves 80% power assuming a one-sided exact test and a one-sided α -level of 0.025. If at least 4 of the total 21 evaluable patients enrolled in the cohort achieve a response, the statistical basis of evidence will be satisfied.

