1.3 Part 3 Expansion Segment

The primary objective of the Part 3 expansion segment is ORR defined as Complete Response (CR) and Partial Response (PR) of the RP2D regimen of TK216 administered intravenously via continuous infusion through a central venous catheter in patients with relapsed or refractory ES. (includes patients with Ewing sarcoma family of tumors-ESFT). The RP2D regimen may include use of vincristine, a standard therapy for Ewing sarcoma.

Secondary objectives of the Expansion Cohort segment of the study are to assess:

- Progression-Free Survival (PFS) defined as time from first dose of TK216 to tumor progression or death due to any cause
- Overall Survival (OS) defined as time from first dose of TK216 to death due to any cause
- Duration of response (DOR) as defined from the first date a response is identified (either CR or PR) until the date of disease progression
- Disease Control (DC) defined as the proportion of patients with a confirmed Complete Response (CR), Partial Response (PR) or Stable Disease (SD)
- Duration of Disease Control defined as first date of disease control identified (either CR, PR or SD) until the date of progression
- Safety and tolerability of TK216 alone and combined with vincristine as characterized by Adverse Event type, severity, timing and relationship to study drug, as well as laboratory abnormalities
- Exploratory biomarker development to enable prediction of drug toxicity, tumor response and the mechanism(s) of acquired study drug resistance.
- Pharmacodynamics of TK216 on molecular targets in surrogate tissue
- Pharmacokinetics (PK) of TK216 alone and when combined with vincristine

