8.9 Quality control

The sponsor, or its representative, will be responsible for implementing and maintaining quality assurance and quality control systems with written SOPs to ensure that the study is conducted and data are generated, documented (recorded), and reported in compliance with the protocol, cGCP and the applicable regulatory requirements.

9 Statistical Considerations

The clinical outcomes, laboratory, PK, and other safety data from all segments of the study will be analyzed descriptively. In addition to determining DLT and RP2D, results will be analyzed to

determine if a sufficient response signal and safety profile justifies further study. Descriptive statistical summaries for demographic and patient baseline characteristics will be produced, as well as statistical summaries of safety, efficacy and pharmacokinetic/pharmacodynamic results, where categories for statistical summaries will consist of the dose level and duration initially assigned for Parts 1 and 2 dose and schedule escalation, and the initial dose and duration in the Expansion Cohort (RP2D). In addition, exploratory analyses of both toxicity, response (ORR), Stable Disease (SD) and pharmacodynamic data will be performed for both the assigned and actual daily dose and duration of infusions, the actual number of days of treatment, and for cumulative exposure to study drug as expressed by the product sum of dose over time (area under the dose-time curve).

Disease Control Rate (DCR) defined as the proportion of patients with a confirmed Complete Response (CR), Partial Response (PR) or Stable Disease (SD) per RECIST v1.1 Duration of Response (DOR) defined from the first date a response is identified (either CR or PR) until the date of objective tumor progression per RECIST v1.1 Progression-Free Survival (PFS) defined as time from first dose of TK216 to objective tumor progression per RECIST v1.1 or death due to any cause, whichever occurs first.

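### Part 3 has ORR (CR+PR) as its primary objective, but its only evidence rule (4 of 18) also counts durable stable disease, so meeting the rule does not by itself show a given ORR

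*Combined protocol and SAP*

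**What the plan says.** Section 1.3 opens with the objective: "The primary objective of the Part 3 expansion segment is ORR defined as Complete Response (CR) and Partial Response (PR"). Its secondary list has two disease-control items. One is "Disease Control (DC) defined as the proportion of patients with a confirmed Complete Response (CR), Partial Response (PR) or Stable Disease (SD"), which sets no minimum duration for SD. The other is "Duration of Disease Control defined as first date of disease control identified (either CR, PR or SD) until the date of progression", which is a time and not a proportion.

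Section 9.3 gives the Part 3 rule: at least 4 of 18 patients enrolled at the RP2D must "achieve a response or have stable disease for at least 3 months". It continues: "This schema will use a promising ORR/SD of 30% and an uninteresting ORR/SD of 10" per cent, with one-sided alpha 0.10 and power 80%. It closes with: "Note that durable stable disease of 30% is also a promising outcome".

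The Part 4 rule in the same section counts responses alone: "If at least 4 of the total 21 evaluable patients enrolled in the cohort achieve a response", with ORR rates of 5% and 25%.

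The opening text of section 9 says that outcomes are analysed descriptively and that results will be used to "determine if a sufficient response signal and safety profile justifies further study". It already makes the Expansion Cohort, by its initial dose and duration, a category for the efficacy summaries. Sections 9.7 and 10.6 say that CR or PR will be summarised. Section 9.7 specifies confidence intervals for time-to-event data only.

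**The concern.** The primary objective and the evidence rule count different events. ORR excludes stable disease, and the rule includes it if it lasts 3 months. Neither disease-control item in section 1.3 is the event that the rule counts, so the criterion with the alpha and power attached matches no named Part 3 endpoint. ORR, the named primary endpoint, has no null rate, target, threshold or interval in Part 3.

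At stake is what a Part 3 pass can be said to show. Four patients with durable stable disease and no responder would meet the rule in a segment whose primary objective is response. The closing note on durable SD adds some ambiguity: its "also" could be read to mean that 30% is a target for ORR in its own right. Whether durable SD is a reasonable basis for further study is a separate matter and is not questioned here.

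**Working it through.** **Inputs.** From section 9.3: n = 18, pass if 4 or more, null 10%, target 30%, one-sided alpha 0.10, power 80%. From section 1.3: ORR = CR + PR. The documents give no rate for durable SD, nor ORR-only rates for Part 3, so the rates in step 4 are assumptions.

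**1. The plan's own figures.** Let X be the number of patients with the composite event, X ~ Bin(18, p).

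- Alpha = P(X ≥ 4 | p = 0.10) = 1 − (0.1501 + 0.3002 + 0.2835 + 0.1680) = 0.098.
- Power = P(X ≥ 4 | p = 0.30) = 1 − (0.0016 + 0.0126 + 0.0458 + 0.1046) = 0.835.

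Both meet the stated limits. A cut-off of 3 gives alpha 0.266 and a cut-off of 5 gives power 0.667. A search for the smallest single-stage exact design within those limits returns 18 and 4. The design is correct for the composite.

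**2. Carry-over to ORR.** The pass probability depends only on the sum p = ORR + durable-SD rate. With true ORR 0%, the rule passes with probability 0.098, 0.499 and 0.835 when durable SD is 10%, 20% and 30%. Alpha and power therefore apply to ORR only if the durable-SD rate is zero, or if the rule is restricted to responses and 10% and 30% are declared as ORR rates.

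**3. What a pass at exactly 4 of 18 says about ORR.** It can contain 0 to 4 responses. Exact (Clopper-Pearson) two-sided 95% intervals, n = 18:

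| Responses | Observed ORR | 95% CI |
|---|---|---|
| 0 | 0% | 0% to 18.5% |
| 1 | 5.6% | 0.1% to 27.3% |
| 2 | 11.1% | 1.4% to 34.7% |
| 3 | 16.7% | 3.6% to 41.4% |
| 4 | 22.2% | 6.4% to 47.6% |

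For 0 responses the upper limit is 1 − 0.025^(1/18) = 0.185.

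**4. How often a pass contains no response.** With true ORR π and durable-SD rate σ,

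P(no response and at least 4 durable SD) = (1 − π)^18 × P(Bin(18, σ/(1 − π)) ≥ 4).

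Example, π = 0.10 and σ = 0.20: 0.9^18 = 0.1501; P(Bin(18, 0.2222) ≥ 4) = 0.5914; product 0.0888. All passes: P(Bin(18, 0.30) ≥ 4) = 0.8354. Share = 0.0888/0.8354 = 11%.

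| Assumed ORR / durable SD | P(pass, no response) | P(pass) | Share of passes |
|---|---|---|---|
| 20% / 10% | 0.003 | 0.835 | 0.4% |
| 15% / 15% | 0.021 | 0.835 | 2.5% |
| 10% / 5% | 0.002 | 0.280 | 1% |
| 10% / 10% | 0.020 | 0.499 | 4% |
| 10% / 20% | 0.089 | 0.835 | 11% |
| 5% / 10% | 0.045 | 0.280 | 16% |
| 5% / 25% | 0.293 | 0.835 | 35% |
| 0% / 30% | 0.835 | 0.835 | 100% |

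The last row is 100% by construction, because ORR is set to zero.

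**The case against.** The strongest reply is that the plan makes no false claim. Section 9.3 states the event openly and attaches the rates, alpha and power to ORR/SD. It gives the purpose as preliminary evidence to justify further study, and section 9 calls the analysis descriptive. Nothing there calls 4 of 18 a test of ORR; the statement that the size was chosen to support the primary objective appears for Part 4 only. A go/no-go rule broader than the primary endpoint is a legitimate choice. All of this stands.

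Three stronger readings are therefore not supported:

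- A reader might infer that the sample size or error rates are wrong. They are right for the composite.
- A reader might infer that the plan hides which event the alpha and power refer to. The text gives it; only an explicit statement that they do not refer to ORR is missing.
- A reader might infer that Part 3 responses would be lost in the pooled RP2D summary of section 9.7. Section 9 already makes the Expansion Cohort its own efficacy category, so a count of 0 responders would be visible.

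It is also fair that the intervals in step 3 are a consequence of n = 18 under any rule, and that a zero-response pass is rare in the scenarios with ORR of 15% or 20%.

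What remains is that the one rule with a stated evidential standard for Part 3 can be met without any response, and nothing links that rule to the primary objective or sets it apart from it. Section 9 frames the decision as one about a response signal together with safety, which a pass on stable disease alone would not supply.

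**Conclusion.** The mismatch is real and minor. The Part 3 rule is sound for response or SD of at least 3 months, but that composite is not a listed Part 3 endpoint, and a pass does not by itself show a given ORR. In the limiting case the rule is met with 0 of 18 responses, which leaves ORR anywhere from 0% to 18.5%.

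The practical size depends on rates that the documents do not give. In the scenarios with a true ORR of 10% or more, a zero-response pass makes up 0.4% to 11% of passes. It becomes common only when ORR is low and durable SD frequent (35% of passes at 5% with 25%). The calculation assumes 18 independent patients, each with a response, durable SD or neither.

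**What to change.** 1. In sections 1.3 and 9.3, name CR, PR, or SD of at least 3 months as the Part 3 go/no-go criterion, distinct from the ORR primary objective. State that meeting it does not by itself establish an ORR.
2. Add an exact two-sided 95% CI for ORR to the Expansion Cohort summary that section 9 already plans.

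The cost is a few sentences and one interval in a table. The sample size of 18, the threshold of 4, alpha, power, data collection and assessments do not change. Because the rule itself is untouched, the edit is possible whether or not Part 3 has enrolled, which the documents do not say. The one downside is that a pass can no longer be read as success on ORR.

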9.4 Safety

All patients who receive any amount of study drug will be included in the safety analyses. All adverse events will be mapped to preferred terms and system organ classes using the MedDRA dictionary. Patient incidence of adverse events will be displayed by dose group and by system organ class. Adverse events will also be summarized by severity and relationship to study drug. Patient incidence of serious adverse events will also be summarized. The type and number of DLTs will be separately presented by dose group, as appropriate.

Laboratory parameters will be summarized using descriptive statistics at baseline and at each post-baseline time point. Changes from baseline will also be summarized.

9.5 Pharmacokinetics

Pharmacokinetic parameter values will be summarized by descriptive statistics at each dose level. Analysis of variance (ANOVA) for the enantiomer of TK216 only will be used to compare the dose normalized PK parameters (dnC_{max} , $dnAUC_{inf}$, $dnAUC_t$) and $t_{1/2}$ across dose levels. A non-parametric test for the enantiomer of TK216 only will be used to compare T_{max} across dose levels.

9.6 Pharmacodynamics

Pharmacodynamic variables will be summarized by dose group and time point. Correlations between pharmacodynamic variables and efficacy variables may also be performed.

9.7 Efficacy

A modified intent to treat (mITT) approach will be used for efficacy analysis, in which the mITT population will consist of all patients who receive at least a partial dose of study therapy (i.e., any portion of the continuous infusion). Tumor response rates will be summarized by dose group and for all patients who receive the RP2D, including those from the dose and schedule escalation and expansion phases. Responses will be classified as CR, PR, SD or PD according to RECISTv.1.1 criteria. Summaries will be based on the best response recorded up until disease progression. Patients who discontinue prior to the first protocol-scheduled response assessment post first infusion will be considered as non-responders in the primary efficacy analysis. Objective tumor response (CR or PR) will also be summarized, as will PFS, OS, DCR and duration of response and DCR. Time to event data will be summarized by Kaplan-Meier methods, including 25th, 50th (median) and 75th percentiles with point estimates and two-sided 95% confidence intervals, as well as number and percent of censored observations.

10 Statistical analysis

The statistical analyses will be reported using summary tables, figures, and data listings. Continuous variables will be summarized with means, standard deviations, medians, minimums, and maximums. Categorical variables will be summarized by counts and by percentage of patients in corresponding categories. All raw data obtained from the case report forms as well as any derived data will be included in data listings. All analyses will be based on the Safety Population, which will include all patients who receive any amount of study drug.

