1.4 Part 4: Dose and Schedule Evaluation Segment

Primary Objective:

The primary objective of the Part 4 dose and schedule evaluations segment is to assess ORR defined as Complete Response (CR) and Partial Response (PR), per RECIST v1.1, at a starting dose of 175 mg/m²/day of TK216 administered intravenously via continuous infusion over 28-days in patients with relapsed or refractory Ewing Sarcoma.

Secondary Objectives:

- Duration of response (DOR) per RECIST v1.1
- Disease control rate (DCR) per RECIST v1.1
- Progression free survival (PFS) per RECIST v1.1
- Overall survival (OS)
- Safety and tolerability of TK216 alone as characterized by AE type, severity, timing and relationship to study drug, as well as laboratory abnormalities

- Pharmacodynamics of TK216; Exploratory biomarker development to enable prediction of drug toxicity, tumor response and the mechanism(s) of acquired study drug resistance
- Pharmacokinetics of TK216 alone

2. Study Design

TK216-01 is a multicenter, open-label, Phase 1/2 study in which the safety and efficacy of TK216 will be evaluated in patients with relapsed or refractory ES (including patients with ESFT).

Once an appropriate patient has been identified, a 30-day screening period will begin to evaluate eligibility using the defined study inclusion and exclusion criteria.

The study will be executed in several Parts:

- **Part 1:** Dose Escalation Segment (Cohorts 1-6)
- **Part 2:** Schedule Escalation Segment (Cohorts 7-9)
- **Part 3:** Expansion Segment (Cohort 10)
- **Part 4:** Dose and Schedule Evaluation Segment (Cohort 11)

All patients will be treated until objective tumor progression per RECIST v1.1., withdrawal of consent, unacceptable toxicity, study termination by sponsor, or a maximum of 2-years. Patients may receive supportive care for bone marrow and/or gastrointestinal adverse events (e.g., with growth factors, antidiarrheals, antiemetics) and prophylaxis for established toxicities that are recurrent.

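### The plan does not say whether responses counted in the primary ORR and the 4-of-21 rule must be confirmed, or which definition the 5% and 25% rates use

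*Combined protocol and SAP*

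**What the plan says.** All references are to the combined protocol and SAP.

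- **Primary endpoint.** Section 1.4 sets the Part 4 objective as to "assess ORR defined as Complete Response (CR) and Partial Response (PR), per RECIST v1.1". Section 1.3 also defines the Part 3 ORR as CR and PR. Neither mentions confirmation.
- **Decision rule.** Section 9.3 sets the Part 4 pass mark: "If at least 4 of the total 21 evaluable patients enrolled in the cohort achieve a response". The rates are 5% (null) and 25% (hypothesised), and the claim is that "a sample size of 21 patients achieves 80% power assuming a one-sided exact test and a one-sided α -level of 0.025". No source is given for either rate, and nothing says whether they refer to confirmed responses.
- **Derivation of response.** Section 9.7 says "Responses will be classified as CR, PR, SD or PD according to RECISTv.1.1 criteria" and then "Summaries will be based on the best response recorded up until disease progression". Section 10.6 repeats the second sentence.
- **Disease control.** The opening text of Section 9 defines the disease control rate as "the proportion of patients with a confirmed Complete Response (CR), Partial Response (PR) or Stable Disease (SD) per RECIST v1.1". Section 1.3 uses similar wording for Part 3. The Part 4 objective in Section 1.4 lists disease control rate without the word *confirmed*.
- **Duration of response.** The opening of Section 9 starts the clock when a CR or PR is first seen, with no confirmation condition.
- **Scans.** Section 4.1.6.6 schedules Part 4 imaging about every 8 weeks. It describes no separate confirmatory scan.

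**The concern.** The authors used *confirmed* for a secondary endpoint and left it out of the primary endpoint, the best-response sentence and the pass mark. Take a patient with a PR at week 8 and progression at week 16. The best response before progression is PR, so on a literal reading the patient is a responder. An analyst who holds that RECIST v1.1 requires confirmation would not count that patient. Two analysts could therefore report different primary results from the same data.

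This matters because the study is open-label and single-arm, and the Part 4 conclusion turns on one patient: 3 of 21 fails and 4 of 21 passes. No central reading of scans is described. Section 2.5 refers to the investigator's view of response, but for the dose-increase decision; the plan does not say who reads scans for ORR. Taking the best of several reads, with no requirement that it be sustained, pushes the observed rate up. If the definition is left open, it may be settled after the data are seen.

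**Working it through.** **Inputs** (Section 9.3): n = 21, pass mark 4, null rate 5%, hypothesised rate 25%, one-sided exact test, level at most 0.025.

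**Formula.** P(X ≥ 4) = 1 − Σ C(21,k) p^k (1−p)^(21−k), summed over k = 0 to 3.

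**Step 1: the plan's own figures.**
- p = 0.05: 1 − (0.3406 + 0.3764 + 0.1981 + 0.0660) = 1 − 0.9811 = **0.0189**.
- p = 0.25: 1 − (0.0024 + 0.0166 + 0.0555 + 0.1172) = 1 − 0.1917 = **0.808**.
- A pass mark of 3 would give 0.085 under the null, so 4 is the smallest valid cut-off. Over n = 17 to 25, n = 21 is the smallest that reaches 80% power with the level held.

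The design reproduces. In an exact test 0.025 is a ceiling, so an attained 0.0189 is not a discrepancy.

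**Step 2: how much slack there is.** The same formula with other null rates of *counted* responses:

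| Null rate of counted responses | P(at least 4 of 21) |
|---|---|
| 5% | 0.0189 |
| about 5.45% | 0.025 |
| 6% (assumed) | 0.034 |
| 7% (assumed) | 0.055 |

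The margin is 5.45 − 5 = 0.45 percentage points.

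**Step 3: which definition goes with which rate.** Let s be the share of recorded responses that are later confirmed. The documents give no value, so 90% and 80% are assumed.

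| Basis of the 5% and 25% | Responses counted | Level | Power |
|---|---|---|---|
| Either definition | The same definition | 0.0189 | 0.808 |
| Confirmed | All recorded | 0.027 (null 5/0.9 = 5.6%); 0.039 (null 5/0.8 = 6.25%) | above 0.808 |
| Recorded | Confirmed only | 0.013 (s = 90%); 0.0089 (s = 80%) | 0.73 (25 × 0.9 = 22.5%); 0.63 (25 × 0.8 = 20%) |

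In the second row the level passes 0.025 once s falls below about 0.05/0.0545 = 92%.

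**Step 4: Part 3.** Its rule of 4 of 18 (Section 9.3) counts a response or stable disease of at least 3 months. A patient whose response is not confirmed may still qualify through stable disease, so no effect on that rule is computed. The point for Part 3 concerns the ORR endpoint itself.

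**The case against.** A reader might infer that the plan deliberately counts unconfirmed responses. It does not say that. Section 9.7 classifies responses by RECIST v1.1 in the sentence just before the best-response sentence, and Section 1.4 ties the Part 4 ORR to the same standard. The best-response sentence can be read as setting only a time window. The text of RECIST v1.1 is not in the documents, so whether it settles confirmation here cannot be decided from them. The plan is silent on the matter. This part of the objection stands. It does not remove the ambiguity: the disease control definition in Section 9 cites RECIST v1.1 and still adds *confirmed*, which invites the reading that the citation alone was not thought to carry that requirement.

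A reader might also infer that the 0.025 level is not protected. That is not shown. The exact test gives 0.0189 under any definition of response, provided the 5% null refers to that definition. Inflation needs the further assumption that 5% is a confirmed rate while unconfirmed responses are counted. This stands in full.

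The contrast with disease control is weaker than it looks. *Confirmed* may qualify only CR, and a patient with an unconfirmed PR might still enter disease control as stable disease. No conflict in counts is demonstrated.

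Finally, Section 9 calls the analyses descriptive, and Section 9.3 aims only at early evidence to justify further study. That limits the consequences. But Section 9.3 also sets a level and a pass mark, so the definition of response still decides the outcome.

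**Conclusion.** The point holds as a gap in the definition. ORR, best response, duration of response and the 4-of-21 rule carry no stated confirmation requirement. The literal reading lets an unsustained PR count, and that reading biases ORR upward relative to a confirmed rate. The plan also does not tie its 5% and 25% rates to a definition.

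The stated operating characteristics (0.0189 and 0.808) are correct when rates and counted responses share one definition. If they do not, the level passes 0.025 above a null rate of about 5.45%. The values at 6% and 7% illustrate the sensitivity and are not estimates, because the documents give no confirmation share.

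The power figures of 0.73 and 0.63 should not be read as a harm of the current plan. They are a conditional cost of requiring confirmation if 25% was planned as an unconfirmed rate. They also rest on the opposite assumption about the planned rates from the inflation figures, so the two sets cannot both apply.

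**What to change.** 1. Define response for the Part 4 ORR, the 4-of-21 rule and the Part 3 ORR as a best overall response of CR or PR confirmed at the next scheduled scan. In Part 4 that scan is already due about 8 weeks later. Count responses that are not confirmed as non-responses, and report unconfirmed ORR as supportive.
2. Put this definition in Sections 1.3, 1.4, 9.3, 9.7 and 10.6, and use it for duration of response and disease control. In the disease control definition, state which categories *confirmed* qualifies and how an unconfirmed response is counted.
3. State in Section 9.3 that 5% and 25% are confirmed-response rates. The sample size of 21 and the cut-off of 4 then stand, with level 0.0189 and power 0.808.
4. If 25% was in fact planned as an unconfirmed rate, restate the power: 0.73 if 90% of responses confirm and 0.63 if 80% do (both assumed).

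**Cost.** Wording changes only, with no added scans or patients. The reported ORR may be lower, the read-out may wait one scan interval, and item 4 may show that the design has less power than stated.
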